The information provided in this document is strictly confidential and is intended solely for the guidance of the clinical investigation. Reproduction or disclosure of this document whether in part or in full to parties not associated with the clinical investigation, or its use for any other purpose, without the prior written consent of the sponsor is not permitted.

Throughout this document, symbols indicating proprietary names (®, TM) may not be displayed. Hence, the appearance of product names without these symbols does not imply that these names are not protected.

¹ The study population was modified via Amendment 4 (see Section 16.2.2.1)

² The sponsor information was changed via Amendment 5 (see Section 16.3.2.1)

³ The medical expert was changed via Amendments 4 and 5 (see Section 16.2.2.1 and 16.3.2.1)

Signature of Bayer's medically responsible person

The signatory agrees to the content of the final clinical study protocol as presented.

Name: PPD [Redacted]

Role: PPD [Redacted]

Date: November 15th 2016

Signature: PPD [Redacted]

Signature of the investigator

The signatory agrees to the content of the final clinical study protocol as presented.

Name:

Affiliation:

Date:

Signature:

Signed copies of this signature page are stored in the sponsor's study file and in the respective center's investigator site file.

Synopsis - amended

Title	7-day study of the safety, efficacy and the pharmacokinetic and pharmacodynamic properties of oral rivaroxaban in children from birth to less than 6 months with arterial or venous thrombosis ⁴
Short title	EINSTEIN Junior Phase I/II in children from birth to less than 6 months
Clinical study phase	I/II
Study objectives	
The primary objective is:
 
 to characterize the pharmacokinetic/pharmacodynamic profile of a 7-day treatment with oral rivaroxaban 
The secondary objectives are:
 
 to assess the incidence of major bleeding and clinically relevant non-major bleeding, to assess the incidence of symptomatic recurrent thromboembolism and to assess asymptomatic deterioration in the thrombotic burden on repeat imaging
Test drug/ active ingredient	Rivaroxaban
Dose(s)	Age- and body weight-adjusted three times daily dosing of rivaroxaban to achieve a similar exposure as that observed in adults treated for venous thromboembolism (VTE) with 20 mg rivaroxaban once daily ⁵
Route of administration	Oral suspension
Duration of treatment	7 days
Indication	Children from birth to less than 6 months with documented symptomatic or asymptomatic arterial or venous thrombosis ⁶
Diagnosis and main criteria for inclusion /exclusion	
Children from birth to less than 6 months with documented symptomatic or asymptomatic arterial or venous thrombosis who have been treated with anticoagulant therapy for at least five days. ⁷
 
Inclusion
 
 Children from birth to less than 6 months with documented symptomatic or asymptomatic venous or arterial thrombosis who have been treated with anticoagulant therapy for at least 5 days. ⁸ Gestational age at birth of at least 37 weeks. Hemoglobin, platelets, creatinine, alanine aminotransferase (ALT) and total and direct bilirubin assessed within 10 days prior to enrollment.

⁴ The study population was modified via Amendment 4 (see Section 16.2.2.2)

⁵ The dosing was changed from b.i.d. to t.i.d. via Amendment 5 (see Section 16.3.2.2)

⁶ The study population was modified via Amendment 4 (see Section 16.2.2.2)

⁷ This section was modified via Amendment 4 (see Section 16.2.2.2)

⁸ Inclusion criterion 1 was changed via Amendment 4 (see Section 16.2.2.2)

	
4. Oral feeding/nasogastric/gastric feeding for at least 10 days.
 
5. Informed consent provided.
 
6. Body weight >2600 g.⁹
 
Exclusion
 
1. Active bleeding or high risk for bleeding contraindicating anticoagulant therapy, including history of intra-ventricular bleeding
 
2. Symptomatic progression of thrombosis during preceding anticoagulant treatment
 
3. Planned invasive procedures, including lumbar puncture and removal of non-peripherally placed central lines during study treatment
 
4. Hepatic disease which is associated with either: coagulopathy leading to a clinically relevant bleeding risk, or alanine aminotransferase (ALT) > 5x upper level of normal (ULN) or total bilirubin (TB) > 2x ULN with direct bilirubin > 20% of the total
 
5. Creatinine > 1.5 times of normal
 
6. Uncontrolled hypertension defined as > 95th percentile^a ¹⁰
 
7. History of gastrointestinal disease or surgery associated with impaired absorption
 
8. Platelet count <100 x 10⁹/L
 
9. Concomitant use of strong inhibitors of both cytochrome P450 isoenzyme 3A4 (CYP3A4) and P-glycoprotein (P-gp), e.g. all human immunodeficiency virus protease inhibitors and the following azole-antimycotics agents: ketoconazole, itraconazole, voriconazole, posaconazole, if used systemically (fluconazole is allowed) ¹¹
 
10. Concomitant use of strong inducers of CYP3A4, e.g. rifampicin, rifabutin, phenobarbital, phenytoin and carbamazepine ¹²
 
11. Indication for anticoagulant therapy other than current thrombosis
 
12. An indication for continued antiplatelet therapy or non-steroid anti-inflammatory drug (NSAID) therapy. Incidental use is allowed. ¹³
 
13. Hypersensitivity to rivaroxaban or its excipients
 
14. Participation in a study with an investigational drug or medical device within 30 days prior to enrollment.
 
^a See Appendix 17.1.2

Study design	Non-randomized, open label, multicenter, combined single and multiple dose study

⁹ Inclusion criterion 6 was added via Amendment 1 (see Section 16.1.2.1)

¹⁰ Exclusion criterion 6 was modified via Amendment 4 (see Section 16.2.2.2)

¹¹ Exclusion criterion 9 was modified via Amendment 1 (see Section 16.1.2.1)

¹² Exclusion criterion 10 was modified via Amendment 1 (see Section 16.1.2.1)

¹³ Exclusion criterion 12 was modified via Amendment 4 (see Section 16.2.2.2)

Methodology	
Children with confirmed arterial or venous thrombosis who have been treated with anticoagulant therapy for at least five days.¹⁴
 
Children will receive an age- and body weight-adjusted rivaroxaban regimen using an oral suspension (1 mg/mL) for a total of 7 days followed by an observational period of another 30 days. Rivaroxaban will be administered three times daily.¹⁵
 
An ultrasound will be performed at day 1 and 8 of rivaroxaban treatment to document asymptomatic changes. In addition, children will be monitored for the occurrence of symptomatic recurrent thrombosis and bleedings. All suspected clinical study outcomes and baseline and repeat ultrasound imaging tests will be assessed by a Central Independent Adjudication Committee (CIAC).
 
An independent data monitoring committee (DMC) will monitor the children's safety and give recommendations to the steering committee.

Number of subjects	At least 8 children will be included.
Primary outcome	Results of pharmacokinetics (PK) / pharmacodynamics (PD) (prothrombin time, activated partial thromboplastin time and anti-factor Xa activity)
Secondary outcomes	Composite of major and clinically relevant non-major bleeding. Composite of all symptomatic recurrent thromboembolism and asymptomatic deterioration in thrombotic burden on repeat imaging.
Plan for statistical analysis	The incidence of the composite of major and clinically relevant non-major bleeding and the incidence of symptomatic recurrent thromboembolism, and asymptomatic deterioration in thrombotic burden on repeat imaging will be summarized. Quantitative data will be described by summary statistics. Results of PK/PD analyses will be provided.

¹⁴ This section was changed via Amendment 4 (see Section 16.2.2.2)

¹⁵ The dosing was changed from b.i.d. to t.i.d. via Amendment 5 (see Section 16.3.2.2)

Table 1: Flow chart: study visits ¹⁶

Visit	Screen ^a	Treatment period			30 day post study treatment contact
	1	2	3	4	5
Days	Day -10 to Day 1	Day 1	Day 3	Day 8	Day 37+ 7 days
Obtain informed consent	•				
Check in-/exclusion criteria	•				
Obtain demographic data	•				
Check medical history	•	•			
Record anticoagulant medication	•	•			
Obtain blood pressure	•				
Obtain body weight	•	•	•		
Check Hb, platelets, creatinine, ALT, total and direct bilirubin	• ^b				
Obtain ALT, total and direct bilirubin				•	
Re-confirm in-/exclusion criteria		•			
Obtain INR, if receiving VKA ^f		•			
Enroll patient		•			
Dispense study medication Instruct how to administer the study medication Provide study booklet Provide rivaroxaban oral suspension handling guidelines		• ^c			
Record all concomitant medication		•	•	•	•
Collect baseline imaging ^d	•				
Repeat ultrasound imaging ^d		•		• ^e	
Check for study outcomes ^d			•	•	•
Check adverse events		•	•	•	•
Check drug accountability and compliance				•	
Check if anticoagulant treatment continued after Visit 4					•
Complete eCRF	•	•	•	•	•

ALT = alanine aminotransferase, eCRF = electronic case report form, Hb = hemoglobin; INR= international normalized ratio, VKA= vitamin K antagonist

^a The screening visit can be performed up to 10 days prior to inclusion into the study.

^b Hb, platelets, creatinine, ALT, total and direct bilirubin results should be available within 10 days prior to inclusion into the study. If results are not available, obtain blood sample.

^c If child discharged from the hospital.

^d Compile adjudication package and send it to the adjudication office.

^e Repeat ultrasound can be obtained on Day 8 ± 1.

^f INR should be below 2.5 before starting rivaroxaban (see Section 5.1.1.3).

¹⁶ The study flow chart was modified via Amendment 1 (see Section 16.1.2.1)

Table 2: Flow chart: pharmacokinetics and pharmacodynamics ¹⁷

PK and PD ^a	Visit 1	Visit 2			Treatment day 2			Visit 3			Treatment day 4 to 7			Visit 4
Rivaroxaban treatment days	Screen day -10 to day 1	Treatment day 1			Treatment day 2			Treatment day 3			Treatment day 4 to 7			Day 8
Rivaroxaban administration		1 st dose	2 nd dose	3 rd dose	1 st dose	2 nd dose	3 rd dose	1 st dose	2 nd dose	3 rd dose	1 st dose	2 nd dose	3 rd dose	
PK/PD time points		0.5 to 3 hr post dose	7 to 8hr post dose					0.5 to 3 hr post dose	7 to 8hr post dose					10-16 hr after last dose at day 7
Obtain blood sample for PK ^b		•	•					•	•					
Obtain blood sample for PD ^c			•					•						• ^d

hr = hour(s), PD = pharmacodynamics, PK = pharmacokinetics
^a The approximate total blood volume taken per child for PK/PD is 6.6 mL. Always draw the PD sample as the last sample.
^b Blood volume per PK sample is approximately 0.6 mL; total blood volume for all PK samples is 2.4 mL.
^c Blood volume per PD sample is approximately 1.4 mL; total blood volume for all PD samples is 4.2 mL.
^d If continued treatment with anticoagulants is necessary, administer the anticoagulant after last sample is taken for rivaroxaban.

Hb	hemoglobin	UFH	unfractionated heparin
IB	investigator's brochure	ULN	upper limit of normal
ICH	International Conference on Harmonization	VKA	vitamin K antagonist
		VTE	venous thromboembolism

1. Introduction - amended

The classical management of venous thromboembolism (VTE) in adults consists of an initial treatment with adjusted-dose intravenous unfractionated heparin (UFH), body weight-adjusted subcutaneous low molecular weight heparin (LMWH), or body weight-adjusted subcutaneous fondaparinux followed by long-term treatment with a vitamin K antagonist (VKA).⁽¹⁾ VKA therapy should be continued for at least three months. The dose of VKA needs to be adjusted to maintain the international normalized ratio (INR) in the therapeutic range (target 2.5, range 2.0-3.0). This therapeutic approach has also been adopted for VTE treatment in children.

Treatment with heparins and VKA has several unsatisfying aspects. For heparins, these include the requirement for intravenous or subcutaneous injection and monitoring of the activated partial thromboplastin time (aPTT). For VKA, these include a slow onset and offset of action, a narrow therapeutic window requiring frequent INR monitoring, and subsequent dose adjustments, caused by food and drug interactions.⁽²⁾ An oral anticoagulant drug that requires no monitoring of its effect, with a rapid onset of action and a high benefit-risk ratio is of considerable interest not only for adults, but especially for the pediatric population.

Rivaroxaban has been extensively studied in the adult population with symptomatic deep vein thrombosis (DVT) and pulmonary embolism (PE). In two dose finding studies,^(3,4) various rivaroxaban dosages were evaluated and compared to standard of care: LMWH and VKA. As a result of these dose finding studies, a rivaroxaban regimen was selected that consisted of 15 mg twice daily treatment for the initial 3 week acute treatment, followed by 20 mg once daily for long-term treatment. Subsequently, this fixed dose rivaroxaban regimen was evaluated in a large phase III study and was compared to body weight-adjusted LMWH and INR titrated VKA in patients with symptomatic deep vein thrombosis. The results demonstrated clear non-inferiority for the primary efficacy outcome and a similar safety profile in terms of the occurrence of major bleeding and clinically relevant non-major bleeding.⁽⁵⁾

The goal of the rivaroxaban pediatric program is to make rivaroxaban available to children for treatment and secondary prevention of VTE. To accomplish this goal, an age- and body weight adjusted dosing regimen has been developed and is being evaluated in a phase III program in children from 6 months to less than 18 years.

Children between birth and less than 6 months will be evaluated within separate studies because of distinct differences in the coagulation system, presentation of venous thrombosis and treatment requirements.

In this phase I/II study, children with confirmed symptomatic or asymptomatic arterial or venous thrombosis will be treated for 7 days with the age- and body weight-adjusted rivaroxaban three times daily dosing regimen to achieve a similar exposure as that observed in adults treated for VTE with 20 mg rivaroxaban once daily.¹⁸

¹⁸ This section was modified via Amendment 4 and 5 (see Sections [16.2.2.3](#) and [16.3.2.3](#))

1.1 Rivaroxaban

Rivaroxaban is an oral, highly selective direct factor Xa inhibitor. Inhibition of factor Xa interrupts the intrinsic and extrinsic pathway of the blood coagulation cascade, inhibiting both thrombin formation and development of thrombi. Rivaroxaban is widely approved for the prevention of VTE following elective hip or knee replacement surgery, for treatment and secondary prevention of DVT and PE, for the primary and secondary prevention of stroke and systemic non-central nervous system (CNS) embolism in non-valvular atrial fibrillation, and for the prevention of atherothrombotic events after an acute coronary syndrome.

1.2 Venous or arterial thrombosis - amended ¹⁹

Compared with adults, thrombosis is rare in children and often is a secondary complication of primary underlying medical conditions or of the use of central lines.⁽⁶⁾

In neonates who have a central line, a high risk of thrombotic events has been observed. Canadian prospective registries estimated an incidence of thrombosis of 24 per 10,000 neonatal admissions, whereas for older children (>1 month old), the incidence is about 5.3 per 10,000 hospital admissions.^(7,8)

A Canadian registry published in 1994 in children aged 1 month to 18 years reported that thrombosis was associated with the use of central venous lines in 33%, with cancer in 23%, with congenital heart disease in 15%, with trauma in 15%, with inherited thrombophilia in 9%, and with infection in 7.5%.⁽⁸⁾ Multiple co-existing risk factors were often present and 39.4% and 35% of children had 2 or 3 concomitant risk factors, respectively.⁽⁸⁾

In 1995, another Canadian registry reported that, except for spontaneous renal vein thrombosis, 89% of thromboses in neonates were associated with the use of central venous or arterial lines. Most of the cases involved the superior caval vein, inferior caval vein, right atrium or femoral veins. Less commonly affected were the brachiocephalic, subclavian, jugular and iliac veins. Arterial thrombosis typically affected the aorta or the iliac and femoral arteries.⁽⁷⁾

1.3 Rationale of the study and risk-benefit assessment - amended

Treatment options are limited to heparins and VKA, which are cumbersome to manage due to the requirement for daily subcutaneous or intravenous injections and regular blood sampling for laboratory monitoring followed by dose adaptations. In children, the availability of an oral anticoagulant treatment that does not require subcutaneous or intravenous injections and regular blood sampling for laboratory monitoring, as is the case in adults, would be desirable.

In adults, rivaroxaban is administered orally and is characterized by stable and predictable pharmacokinetics and, therefore, does not require laboratory monitoring with subsequent dose adjustments. In the Phase III EINSTEIN DVT and PE studies in adults,⁽⁹⁾ rivaroxaban was non-inferior to standard of care with enoxaparin followed by VKA treatment. In the pooled analysis, the incidence of the primary efficacy outcome (the composite of symptomatic

¹⁹ The heading was modified via Amendment 4 (see Section 16.2.2.4)

recurrent DVT, non-fatal and fatal PE) was lower on rivaroxaban than on enoxaparin/VKA treatment, with a similar incidence of clinically relevant bleeding. The comparison against placebo in patients studied for extended treatment of VTE (EINSTEIN extension study) demonstrated clear superiority for rivaroxaban against placebo in all efficacy analyses and across all subgroups. Rivaroxaban was well tolerated and the safety profile, including adverse events and observed laboratory abnormalities, was comparable to enoxaparin/VKA treatment.

As a consequence, the expectation is that the selected rivaroxaban age- and body-weight adjusted dose regimen in children will be safe and efficacious without the need for frequent blood sampling to monitor the anticoagulant activity.

To carefully allow for the evaluation of rivaroxaban in neonates and children younger than 6 months with confirmed symptomatic or asymptomatic arterial or venous thrombosis, we elected to evaluate the selected rivaroxaban dose regimen first in children that have been treated with anticoagulant therapy for at least five days. If this study reveals that the selected rivaroxaban dose regimen results in a similar exposure as that observed with 20 mg rivaroxaban in adults, and safety and efficacy is confirmed, a subsequent study will evaluate the selected rivaroxaban dose regimen for the acute and continued treatment of VTE. ²⁰

2. Study objectives

The primary objective is:

- to characterize the pharmacokinetic/pharmacodynamic profile of a 7-day treatment with oral rivaroxaban

The secondary objectives are:

- to assess the incidence of major bleeding and clinically relevant non-major bleeding
- to assess the incidence of symptomatic recurrent thromboembolism and
- to assess asymptomatic deterioration in the thrombotic burden on repeat imaging

3. Study design - amended

This is a non-randomized, open label, multicenter study evaluating the safety, efficacy and PK/PD profile of a 7-day treatment with age- and body weight-adjusted oral rivaroxaban in neonates and infants younger than 6 months with symptomatic or asymptomatic arterial or venous thrombosis. ²¹

²⁰ This section was modified via Amendment 4 (see Section 16.2.2.5)

²¹ This section was modified via Amendment 4 (see Section 16.2.2.6)

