4.1 Planned number of children

At least eight children are planned to be enrolled in the study.

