4.3 Exclusion criteria - amended

1. Active bleeding or high risk for bleeding contraindicating anticoagulant therapy, including history of intra-ventricular bleeding.
2. Symptomatic progression of thrombosis during preceding anticoagulant treatment.
3. Planned invasive procedures, including lumbar puncture and removal of non-peripherally placed central lines during study treatment.
4. Hepatic disease which is associated with either: coagulopathy leading to a clinically relevant bleeding risk, or alanine aminotransferase (ALT) > 5x upper level of normal (ULN) or total bilirubin (TB) > 2x ULN with direct bilirubin > 20% of the total.
5. Creatinine >1.5 times of normal.
6. Uncontrolled hypertension defined as >95th percentile. ²⁶
7. History of gastrointestinal disease or surgery associated with impaired absorption.
8. Platelet count <100 x 10⁹/L.
9. Concomitant use of strong inhibitors of both cytochrome P450 isoenzyme 3A4 (CYP3A4) and P-glycoprotein (P-gp), e.g. all human immunodeficiency virus protease

²⁴ Inclusion criterion 1 was modified via Amendment 4 (see Section 16.2.2.8)

²⁵ Inclusion criterion 6 was added via Amendment 1 (see Section 16.1.2.2)

²⁶ Exclusion criterion 6 was modified via Amendment 4 (see Section 16.2.2.9)

inhibitors and the following azole-antimycotics agents: ketoconazole, itraconazole, voriconazole, posaconazole, if used systemically (fluconazole is allowed).²⁷

10. Concomitant use of strong inducers of CYP3A4, e.g. rifampicin, rifabutin, phenobarbital, phenytoin and carbamazepine.²⁸
11. Indication for anticoagulant therapy other than current thrombosis.
12. An indication for continued antiplatelet therapy or non-steroid anti-inflammatory drug (NSAID) therapy. Incidental use is allowed.²⁹
13. Hypersensitivity to rivaroxaban or its excipients.
14. Participation in a study with an investigational drug or medical device within 30 days prior to enrollment

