7.8 Determination of sample size

At least 8 children are planned to be enrolled in the study. For the area under the curve (AUC), a geometric coefficient of variation (geom. CV) of about 40% was observed in adults, and was also observed in study 12892 in the age group 12 to 18 years (n=9). In the age cohort 6 to <12 years, an even smaller geometric coefficient of variation was observed. Although it is expected from the model that the variability will be higher in neonates and infants, the exact numbers remain unclear. The sample size of 8 subjects will yield an exploratory 90% confidence interval for the geometric mean AUC-estimate between 50% and 200% of the estimate, provided the geometric coefficient of variation does not exceed 138%, which would be more than a tripling of the variability observed in adolescents. If the geometric coefficient of variation will be 80%, the exploratory 90% confidence interval for the geometric mean AUC-estimate would be located between 62% and 161% of the estimate.

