## 1. Introduction

This SAP is based on the integrated clinical study protocol version 2.0 (21 Jul 2015) and its local amendment 2 for Canada dated 22 September 2015.

The goal of the rivaroxaban pediatric program is to make rivaroxaban available to children for treatment and secondary prevention of VTE. To accomplish this goal, an age- and body weight adjusted dosing regimen has been developed and is being evaluated in a phase III program in children from 6 months to less than 18 years.

Children between birth and less than 6 months will be evaluated within separate studies because of distinct differences in the coagulation system, presentation of venous thrombosis and treatment requirements.

In this phase I/II study, children with confirmed symptomatic or asymptomatic catheter related arterial or venous thrombosis will be treated for 7 days with the age- and body weight-adjusted rivaroxaban twice daily dosing regimen to achieve a similar exposure as that observed in adults treated for VTE with 20 mg rivaroxaban once daily.

Compared with adults, thrombosis is rare in children and often is a secondary complication of primary underlying medical conditions or of the use of central lines.

Treatment options are limited to heparins and VKA, which are cumbersome to manage due to the requirement for daily subcutaneous or intravenous injections and regular blood sampling for laboratory monitoring followed by dose adaptations. In children, the availability of an oral anticoagulant treatment that does not require subcutaneous or intravenous injections and regular blood sampling for laboratory monitoring, as is the case in adults, would be desirable.

To carefully allow for the evaluation of rivaroxaban in neonates and children younger than 6 months with confirmed symptomatic or asymptomatic catheter related arterial or venous thrombosis, we elected to evaluate the selected rivaroxaban dose regimen first in children that have been treated with anticoagulant therapy for at least two weeks. If this study reveals that the selected rivaroxaban dose regimen results in a similar exposure as that observed with 20 mg rivaroxaban in adults, and safety and efficacy is confirmed, a subsequent study will evaluate the selected rivaroxaban dose regimen for the acute and continued treatment of VTE.

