### 6.2 Safety analysis

#### Adverse events

All safety analyses will be performed on the safety population. The analysis will primarily focus on bleeding that occurred during or within 2 days after stop of rivaroxaban. Bleeding events observed later will be described separately. Individual listings of major and clinically relevant non-major bleeding will be provided. The incidence of bleeding will be summarized. If a sufficient number of bleeding events is observed, factors which potentially influence the occurrence of bleeding will be assessed by appropriate statistical procedures. Quantitative data will be described by the summary statistics and will be presented for the original data as well as for the difference to baseline. Frequency tables will be provided for qualitative data.

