### 6.3 Efficacy analysis

All efficacy analyses will be performed on the full analysis set population. The incidence of symptomatic recurrent venous thromboembolism and asymptomatic deterioration in thrombotic burden on repeat imaging will be summarized.

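### Protocol 1.3 and SAP 1 make the next study depend partly on confirmed safety and efficacy, which a single-arm study of at least 8 pre-treated children, with no interval on any event rate, cannot provide

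*Protocol*

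**What the plan says.** The condition for moving on is one sentence in Protocol 1.3 with two parts. It opens with exposure: "If this study reveals that the selected rivaroxaban dose regimen results in a similar exposure as that observed with 20 mg rivaroxaban in adults". It then adds the clinical part: "and safety and efficacy is confirmed, a subsequent study will evaluate the selected rivaroxaban dose regimen for the acute and continued treatment of VTE". SAP 1 carries the same clause: "and safety and efficacy is confirmed, a subsequent study". Neither document says what result would count as confirmation. There is no rate, maximum event count, margin or comparator.

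The operative sections are more modest. The objectives (Protocol 2, SAP 2) are to characterise the PK/PD profile and to assess event incidences. On numbers, Protocol 4.1 states: "At least eight children are planned to be enrolled in the study". Protocol 7.8 justifies that number by PK precision alone: "The sample size of 8 subjects will yield an exploratory 90% confidence interval for the geometric mean AUC-estimate between 50% and 200% of the estimate". This is conditional on a geometric CV of no more than 138%.

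For the clinical outcomes, SAP 6.2 says "The incidence of bleeding will be summarized" and SAP 6.3 says "The incidence of symptomatic recurrent venous thromboembolism and asymptomatic deterioration in thrombotic burden on repeat imaging will be summarized". Protocol 7.4 and 7.5 say the same. SAP 4.1 describes all analyses as descriptive, and its list of statistics contains no interval. The only confidence interval mentioned in either document is the exploratory one for AUC.

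Entry requires at least 5 days of prior anticoagulation (Protocol 4.2). Active bleeding or high bleeding risk is an exclusion, and so is "Symptomatic progression of thrombosis during preceding anticoagulant treatment" (Protocol 4.3).

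**The concern.** To confirm safety and efficacy, a study must be able to rule out unacceptable event rates, or to compare with a control. This one has no control group, was not sized for clinical events, and attaches no measure of uncertainty to the rates it will report. It also observes children who have already had at least 5 days of anticoagulation without symptomatic progression, whereas the study that would follow includes acute treatment.

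What is at stake is how a small number of events, or none, is read when that step is taken. A bare percentage from about 8 children says little, and the plan as written does not show the reader how little. The problem is sharper for the current regimen: five children were treated twice daily before Amendment 5 raised the total daily dose by 50% (Protocol 5.1.1), and nothing in the analysis sections separates the two regimens.

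**Working it through.** **Inputs.** Planned number: at least 8 (Protocol 4.1, 7.8). Children treated twice daily: 5, with no bleeding events (Protocol 5.1.1). Precision figures for AUC: Protocol 7.8. Expected bleeding or thromboembolic rates: none given, so the true rates below are illustrative.

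**Step 1: reproduce the plan's own figure.** On the log scale, sigma = sqrt(ln(1 + CV²)), and the 90% limits relative to the estimate are exp(± t(0.95; 7 df) × sigma / sqrt(8)).
- CV 138%: sigma = 1.0326, giving 50.1% to 199.7% (stated: 50% to 200%). The largest CV that keeps the interval within 50% to 200% is 138.5%.
- CV 80%: sigma = 0.7033, giving 62.4% to 160.2% (stated: 62% to 161%; the 161% is 1/0.62, so the gap is rounding).

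The sample size statement is therefore sound for what it covers, which is AUC only.

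**Step 2: what the same number gives for clinical events.** With zero events in n, the exact two-sided 95% upper limit is 1 − 0.025^(1/n), and the one-sided 95% limit is 1 − 0.05^(1/n). For one event in 8, the Clopper-Pearson limits solve P(X ≥ 1) = 0.025 and P(X ≤ 1) = 0.025.

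| Events / n | Two-sided 95% interval | One-sided 95% upper limit |
|---|---|---|
| 0/3 | 0% to 70.8% | 63.2% |
| 0/5 | 0% to 52.2% | 45.1% |
| 0/8 | 0% to 36.9% | 31.2% |
| 1/8 | 0.3% to 52.7% | 47.1% |
| 0/12 | 0% to 26.5% | 22.1% |

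The 0/12 row shows that a modest excess over the minimum does not change the picture. The 0/5 row is the twice-daily bleeding experience already described in Protocol 5.1.1.

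**Step 3: how often a clean result would occur by chance.** P(0 events) = (1 − p)^n.
- n = 8: 66% at a true rate of 5%, 43% at 10%, 17% at 20%.
- n = 3: 73% at a true rate of 10%.

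To exclude a rate with one-sided 95% confidence when no events occur, n must be at least ln(0.05)/ln(1 − p). That is 14 children for 20% and 29 for 10%.

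**Step 4: the number on the current regimen.** The documents do not say whether the five twice-daily children count towards the 8. If they do, the planned minimum leaves 8 − 5 = 3 on three-times-daily dosing; if they do not, it leaves 8. Under that range (an assumption), the zero-event upper limit at the planned minimum lies between 70.8% and 36.9%.

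**The case against.** The best reply is that this is a sentence of rationale and not an analysis rule. The objectives, the descriptive SAP and the exploratory sample size never claim a confirmatory design. The sentence also puts exposure first, and the rationale for Amendment 5 (Protocol 16.3.1.3) says that matching adult exposure is what permits extrapolation of safety and efficacy from adults. On that reading, confirmation means only that nothing contradicts the expectation built on the adult data.

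Much of this stands. The programme does lean mainly on exposure, and the point must not be read as if the clinical clause were the sole condition. But the two parts are joined by a conjunction, so the second is still required. And if safety and efficacy are to be extrapolated, that is a reason for the sentence not to say that this study confirms them.

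It is also fair that the plan offers more than incidences. It has individual listings of bleeding and adverse events, central adjudication, DMC review, and 30 days of follow-up after treatment. With about 8 children, case-level review will carry much of the judgement. These measures improve the quality of each event record; they do not narrow the uncertainty about a rate. Enrolling pre-treated children first is a deliberate cautious step and is not itself a fault. Finally, a reader can work out the limits from a count. That makes the intervals cheap to add, and does not make them unnecessary.

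**Conclusion.** The point holds as a mismatch between a stated condition and what the design can deliver. With the planned minimum of 8, an event-free result remains compatible with true rates up to 36.9%, and one event with 0.3% to 52.7%. For the three-times-daily regimen alone, the zero-event limit is between 70.8% and 36.9%, depending on the unstated question of whether the five earlier children count.

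Three stronger readings are tempting, and the documents do not support them.
- A reader might infer that zero events is the expected result and would be taken as confirmation. No event rate is given for this population. With 8 children, zero is the single most likely count only if the true rate is below 1/9 (about 11%), from (1 − p) > 8p. The bleeding composite is broad and the efficacy composite includes asymptomatic deterioration. Nothing says that 0% would satisfy the condition.
- A reader might take 3 children on the current regimen as fact. It is the lower end of a range.
- A reader might conclude that the sample size is wrong. It reproduces for its stated PK purpose, and no larger number or hypothesis test is called for here.

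**What to change.** In Protocol 1.3 and SAP 1, keep the exposure condition and replace the confirmation clause with wording the design supports, such as: *no bleeding or thromboembolic finding judged by the DMC and steering committee to preclude further study*. This matches the roles already set out in Protocol 6.14, where the DMC recommends and the steering committee decides.

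In Protocol 7.4 and 7.5 and SAP 6.2 and 6.3, report the bleeding and efficacy incidences with exact (Clopper-Pearson) 95% confidence intervals, separately for the twice-daily and three-times-daily regimens and overall. SAP 3 currently describes only twice-daily dosing, so the split by regimen has to be written in. Stating the zero-event limits in Protocol 7.8 beside the AUC precision is optional.

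The cost is a change of wording and one option in the incidence tables. No estimate, dataset or sample size changes. The downside is that the stated claim becomes less favourable and the intervals will be wide, though that width reflects what the study can show.
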